6.4.1.1. Selection of Target and Non-Target Lesions

Screening/baseline requirement:

Screening MRI evaluations will be performed within 21 days of first dose of study treatment. For subjects on steroids, screening MRI scans **must** be performed while on a stable or decreasing

dose of steroids for at least 5 days. Subjects must have measurable disease (including subjects that have undergone a surgical resection prior to enrollment).

- **Measurable disease** is defined as lesions that are (all criteria below are met):
 - Brain lesions which are the primary tumors
 - Measurable in 2 perpendicular diameters
 - At least twice the slice thickness on MRI (ie, visible on 2 or more axial slices)
Note: MRI should be performed with cuts of 3 mm or less in slice thickness contiguously.
 - Do not include cavity or cyst in measurement (see Section 6.4.1.2)
- **Nonmeasurable disease** is defined as (any criteria below are met):
 - Spinal lesions
 - Lesions with poorly defined margin on MRI
 - Cerebrospinal fluid
 - Cystic or necrotic components (see Section 6.4.1.2)

All target and non-target lesions should be identified and recorded at screening.

- For most CNS tumors, only one lesion/mass is present and therefore this single lesion is considered a “target” for measurement to assess tumor response and progression.
- Spinal lesions should be considered as nonmeasurable disease (ie, non-target lesions); however, size should be noted and change in size should be evaluated.
- All subjects should have at least one measurable, target lesion confirmed by MRI. Target lesions should be selected on the basis of size (eg, largest) and suitability for accurate repeated measurements. All other lesions will be followed as non-target lesions.
- Leptomeningeal tumor spread is usually not a target lesion, and cannot be measured accurately; however, presence and location of leptomeningeal tumor spread should be noted and change in extent/thickness should be evaluated on assessments.

6.4.1.2. Methodology to Determine Tumor Measurement

Tumor dimensions will be determined by two-dimensional measurement of the longest diameter (width [W]) and the longest perpendicular diameter (transverse [T]) for each target lesion (Figure 3). Radiologist at each institution may select the appropriate sequence that best highlights the tumor (T1-weighted postcontrast or T2-weighted or FLAIR) and the same sequence should be used for serial measurements.

Radiographic response determination will be based on a comparison of an area (W x T) between the baseline assessment (or smallest disease measurements recorded since the start of protocol therapy [nadir]) and the assessments post-treatment. Assessments post treatment should reiterate the measurements obtained at baseline for each target lesion.

[figure not shown]
Tumor response criteria are determined by changes in size using the longest tumor diameter and its perpendicular diameter (W x T). The following describes the measurement method:

- The **longest diameter** measurement (W) can be measured from the axial plane or the plane in which the tumor is best seen or measured. The same plane chosen at baseline should be used in subsequent assessments.
- The **perpendicular diameter** measurement (T) is maximal perpendicular to the W in the selected plane.
- The cystic or necrotic components of a tumor are not considered in tumor measurements. Therefore, only the solid component of cystic tumors should be measured. If cyst/necrosis composes the majority of the lesion, the lesion may not be “measurable.” In general, such lesions should be considered non-target.

Options:

- If the cyst/necrosis is eccentric, the W and T of the solid portion should be measured, and the cyst/necrosis portion should be excluded from measurement.
- If the cyst/necrosis is central but represents a small portion of the tumor (< 25%), the cyst/necrosis should be disregarded, and the entire tumor should be measured.
- If the cyst/necrosis is central and represents a large portion of the tumor, identify a solid aspect of the tumor mass that can be reproducibly measured.

Figure 3: Guidelines for Measurement of Tumor Size

Source: Children's Oncology Group (COG) guideline

6.4.1.3. Tumor Response Criteria for Target Lesions

1. Response criteria are assessed in 2 dimensions - the product of W x T
2. The overall measurement of target lesions for a particular assessment is quantified by the sum of the products of the perpendicular diameters of all target lesions (eg, $W_1 \times T_1 + W_2 \times T_2 + \dots$).
3. To assess response/progression, the ratio is calculated:

$$\frac{\text{sum of products } (W_1 \times T_1 + W_2 \times T_2 + \dots) \text{ (current scan)}}{\text{sum of products } (W_1 \times T_1 + W_2 \times T_2 + \dots) \text{ (reference scan)}}$$

4. Radiographic response should be made in comparison to the tumor measurement obtained at baseline for the determination of response, and the smallest tumor measurement (nadir) either at baseline or after initiation treatment for determination of progression.

5. Development of new disease or progression in any established lesions is considered progressive disease, regardless of response in other lesions, eg, when multiple lesions show opposite responses, the progressive disease takes precedence.

The tumor response categories for target lesions are CR, PR, SD and PD and are further defined in [Appendix B](#).

6.4.1.4. Tumor Response Criteria for Non-Target Lesions

The tumor response categories for non-target lesions are CR, incomplete response (IR)/SD and PD and are further defined in [Appendix B](#). Non-target lesions are assessed subjectively and the decision when progression is evident is at the discretion of the radiologist/Investigator.

6.4.1.5. Clinical Status (Neurologic Symptoms/Examination)

The definition of clinical status and deterioration is left to the discretion of the Investigator. Clinical deterioration should be attributable to neurologic abnormalities or worsening neurologic status not explained by causes unrelated to tumor progression (eg, anticonvulsant or corticosteroid toxicity wean, electrolyte disturbances, sepsis, hyperglycemia, etc.) or changes in corticosteroid dose.

6.4.1.6. Corticosteroid Administration

An increase in corticosteroid dose alone will not cause determination of progression in the absence of clinical deterioration or radiographically documented lesion growth. For corticosteroid dose to be considered “stable or decreasing,” it should not be a greater dose than compared with baseline. For overall assessment of response (Section 6.4.1.7), physiologic replacement doses of corticosteroids, defined as no more than 0.75 mg/m²/day of dexamethasone or equivalent, will be considered.

6.4.1.7. Overall Response Assessment

The overall response assessment takes into account response in both target and non-target lesions, the appearance of new lesions, current corticosteroid use (compared to screening/baseline) and neurologic symptoms/examination (clinical status) according to the criteria described in [Appendix C](#).

Subjects who do not meet the criteria for an objective response or disease progression by the end of Cycle 6 (end of Cycle 3 for DIPG subjects) will be considered as having long-term SD.

6.4.1.8. Independent Central Response Review

Response evaluations will be based on MRI results obtained at each site and will be assessed locally and by an independent central reviewer. Corticosteroid use and clinical assessments (ie, neurologic status) will also be considered when determining overall response. The local Investigator’s assessment will be used for subject eligibility and treatment decisions. Efficacy based endpoints incorporating tumor assessments (primary and secondary) will be based on the independent central assessment.

Imaging/response data will be centrally collected and checked for quality by an imaging contract research organization (CRO) designated by Celgene. Independent central review (screening/

baseline and post-baseline assessments) will be performed for all MRIs collected for response assessment. Further details regarding MRI acquisition requirements and image submission procedures are outlined in the Imaging Manual.

Details of the central review process and requirements for central imaging review will be described in the independent review charter. Results of the central review will not be provided to the sites.

6.4.2. Safety and Tolerability Assessments

Safety assessments will consist of monitoring and recording all AEs, including SAEs, concomitant medications, SPMs, dose discontinuations, reductions and interruptions, the regular monitoring of hematology and blood chemistry, regular monitoring of vital signs and physical condition. These assessments should be performed within the prescribed window of the scheduled day of assessment (Table 4) and at any unscheduled visit if clinically indicated; however, AEs, concomitant medications and review for SPMs will be evaluated and recorded continuously throughout the study.

Note: Pomalidomide experience in subjects < 3 years of age is limited. As such, subjects < 3 years of age should be carefully monitored for safety and side effects (adverse effects). In addition, as pomalidomide is metabolized hepatically, subjects with hepatic impairment should also be carefully monitored. In response to any safety concerns in subjects with hepatic impairment, Investigators should have a low threshold for performing additional safety evaluations (ie, hematology, blood chemistry, physical exams, vital signs, etc) as needed.

6.4.2.1. Physical Examinations (Including Vital Signs)

A complete physical examination will include (as applicable) the examination of general appearance, skin, neck, eyes, ears, nose, throat, lungs, heart, abdomen, back, lymph nodes, extremities, vascular and neurological (Section 6.4.2.8). For other indicated areas, based on medical history and/or symptoms, examinations will be performed.

Physical examination will be source documented only; however significant findings that were present prior to the signing of the ICF/IAF must be included in the Medical History page on the subject's eCRF. Clinically significant new findings that begin or worsen after informed consent/assent must be recorded on the AE page of the subject's eCRF.

At screening, the Investigator or designee performing the physical examination will characterize the findings as either normal or abnormal in the source. If abnormal, a description of the abnormality and clinical importance should be source documented. Clinically significant changes from screening/baseline will be recorded in the AE section of the eCRF.

Vital signs assessment will include temperature, blood pressure, heart rate and respiratory rate. On-treatment vital sign measurements will be source documented only; however, if an abnormal (out of range) value is reported at any given visit and clinically significant, that parameter should be collected in the eCRF at every subsequent scheduled visit until it returns to normal or not clinically significant (NCS), and recorded as an AE if appropriate.

6.4.2.2. Height

Height in centimeters (cm) without shoes will be measured. For each height assessment, measurements should be performed three times and the average taken for calculation of BSA.

6.4.2.3. Weight

Body weight (to the nearest 0.1 kilogram [kg] in indoor clothing, but without shoes) will be measured. For each weight assessment, measurements should be performed three times and the average taken for calculation of BSA.

6.4.2.4. Body Surface Area Calculation

Body surface area, in m², will be calculated using the following formula, where weight (W) is in kg and height (H) is in cm (Dubois, 1916):

$$BSA = (W^{0.425} \times H^{0.725}) \times 0.007184$$

The subject's pomalidomide dose should be calculated on the first day of Cycle 1 based upon the subject's current BSA. Measurements of the subject's height and body weight will be repeated on Day 1 of each subsequent cycle and BSA recalculated at these visits.

6.4.2.5. Lansky/Karnofsky Performance Status

For subjects < 16 years of age, the Lansky performance status will be determined. For subjects ≥ 16 years of age, the Karnofsky performance status will be determined (Appendix D). Each subject must continue to be assessed with the same performance status scale used at screening throughout his/her duration in the study (regardless of changing age over time).

6.4.2.6. Laboratory Evaluations

Screening and other laboratory assessments will be performed locally at each scheduled visit according to Table of Events (Table 4) and collection plan in Table 5 below.

Note: Additional assessments should be performed between visits as clinically required to follow AEs or determine dose modifications. All laboratory assessments should be performed prior to treatment administration on that particular visit unless indicated otherwise.

It is the responsibility of the Investigator to obtain and review laboratory results for subject safety, and follow up with subjects in a timely manner. The Investigator will evaluate the clinical significance of each applicable laboratory value outside of the reference range. This decision shall be based upon the nature and degree of the observed abnormality. Values which are considered clinically significant and/or related to study treatment will be noted in source document(s). The Investigator may choose to repeat any abnormal result, in order to rule out laboratory error. "Not clinically significant" or "NCS" will be recorded on the original laboratory sheet for all laboratory values which are outside the reference range, but are judged "not clinically significant." The Investigator making these assessments shall date and initial each form.

Hematology, serum chemistry and viral serology laboratory values will not be collected on the laboratory eCRF; instead, laboratory abnormalities that are considered AEs should be reported on the AE eCRF (see Section 10).

Table 5: Local Clinical Laboratory Parameters Collection Plan

Test Category	Test Name
Hematology	Hematocrit, Hemoglobin, Mean corpuscular volume, Platelets, RBC, White Blood Cells (WBC) absolute and differential (Basophils, Eosinophils, Lymphocytes, Monocytes, Neutrophils)
Chemistry	Albumin, Alkaline phosphatase, ALT (SGPT), AST (SGOT), Bicarbonate, Blood Urea Nitrogen, Calcium, Chloride, Creatinine, Direct Bilirubin, Total Bilirubin, Glucose, Potassium, Phosphorous, Magnesium, Sodium, Total Protein
Viral Serology	Hepatitis B serology is required at screening if status is not known

ALT = alanine aminotransferase; AST = aspartate transaminase; RBC = red blood cell; SGPT = serum glutamic-pyruvic transaminase; SGOT = serum glutamic-oxaloacetic transaminase.

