1.2.4. Pediatric Clinical Trials of Pomalidomide

In the Phase 1 dose escalation trial of pomalidomide monotherapy in children with recurrent, progressive or refractory CNS tumors (PBTC-043), subjects were treated at doses levels of 1.9, 2.6 and 3.4 mg/m²/day on Days 1 through 21 of a 28-day cycle. The maximum tolerated dose (MTD) of 2.6 mg/m²/day was reached with 3 subjects experiencing a total of 4 dose limiting toxicities (DLTs) at the 3.4 mg/m²/day dose level. These DLTs included Grade 4

absolute neutrophil count (ANC) decrease ≥ 5 days during treatment rest period, Grade 3 diarrhea, Grade 3 platelet count decrease and Grade 3 lung infection.

The main toxicity (most commonly reported Grade 3/4 AE) associated with pomalidomide treatment was myelosuppression (decreased neutrophils, platelets, lymphocytes and anemia). Myelosuppression is a known adverse effect of pomalidomide treatment and can be managed effectively with supportive care. Myelosuppression was also the main toxicity observed in the Phase 1 studies of lenalidomide in children with CNS tumors (Warren, 2011; Berg, 2011). The majority of cases observed during the PTBC-043 study resolved without sequelae.

Per protocol, expansion cohorts were initiated with further enrollment at the MTD stratified based on age (< 12 years vs. ≥ 12 years) and steroid use (not on steroids [or on physiologic doses alone] vs. those taking therapeutic doses of steroids). No excessive toxicities or unexpected safety concerns have further been identified. One subject in the expansion cohort experienced a DLT of Grade 4 platelet count decrease; however, per protocol, the criteria for modifying the already identified MTD was not reached. This study is currently ongoing.

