9.7. Safety Analysis

Toxicity Assessment

Toxicity, including SPMs, will be monitored in real time during the course of the study. Descriptive statistics will be used to summarize the proportion of subjects experiencing any Grade 3 or higher non-hematologic toxicities and infections.

Adverse Events

Adverse Events will be coded according to the Medical Dictionary for Regulatory Activities (MedDRA) (latest version). This study will utilize the NCI CTCAE (version 4.03) for toxicity grading and performance reporting. All AE data shall be presented by disease stratum and in aggregate, based on the Safety Population, ie, all subjects receiving at least one dose of pomalidomide.

Treatment-emergent adverse events are defined as any AE occurring or worsening on or after the first dose of the study medication until the 28-day post-treatment Safety Follow-up Visit. All TEAEs, AEs leading to study medication discontinuation, AEs leading to dose reduction/interruption, AEs related to the study treatment, SAEs, and AEs leading to death will be summarized by cycle and 28-day follow-up period after permanent treatment discontinuation as well as by subject (worse recorded grade) per event type (organ class and preferred term) and grade. A summary of AEs with NCI CTCAE (version 4.03) Grade 3 or higher, as well as the most frequent preferred terms, will also be provided by grade and term.

Cross tabulations will be provided to summarize frequencies of abnormalities.

By-subject listings will be provided for all relevant safety data. Graphical displays and figures will be provided where useful to assist in the interpretation of results.

Deaths

Deaths during the Treatment Period (defined as the time between enrollment until the 28-day post-treatment Safety Follow-up Visit) and during the Follow-up Period shall be summarized by frequency of occurrence and corresponding percentage by cause of death per study period (during treatment or follow-up) as well as overall. All death data shall be presented by disease stratum and in aggregate.

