10.3. Abnormal Laboratory Values

An abnormal laboratory value is considered to be an AE if the abnormality:

- results in discontinuation from the study;
- requires treatment, modification/ interruption of the IP dose, or any other therapeutic intervention; or
- is judged to be of significant clinical importance, eg, one that indicates a new disease process and/or organ toxicity, or is an exacerbation or worsening of an existing condition.

Regardless of severity grade, **only** laboratory abnormalities that fulfill a seriousness criterion need to be documented as a SAE.

If a laboratory abnormality is one component of a diagnosis or syndrome, then only the diagnosis or syndrome should be recorded on the AE page/screen of the eCRF. If the abnormality was not a part of a diagnosis or syndrome, then the laboratory abnormality should be recorded as the AE. If possible, the laboratory abnormality should be recorded as a medical term and not simply as an abnormal laboratory result (eg, record thrombocytopenia rather than decreased platelets).

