11. SAFETY ANALYSIS

The purpose of this section is to define the safety parameters for the study. All summaries of safety data will be conducted using the Safety Population and will be presented by tumor type/disease indication, and in aggregate. Safety measurements will include AEs, clinical laboratory information, vital sign measurements, SPM, pregnancy status, and deaths. Individual subject listings will be provided to support the tables.

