- If the numerator is '0' then show '0'. If the denominator is '0', then show 'NA' - apply this logic for descriptive stats;
- All listings will be sorted for presentation in order of tumor type/disease indication, study site, subject number, and date of procedure or event. Subjects who are not enrolled will be listed as a non-enrolled group after enrolled subjects;
- In listings, a day reported in relation to treatment start but which is unknown due to an unknown/partially reported date, will be presented with a hyphen;
- In listings, unknown/missing dates will be reported as 'unknown', while the unknown part of a partial date will be presented as 'UN';
- All tables will be presented by tumor type/disease indication;
- In tables where a parameter/category is displayed over several lines, the statistic will be presented on the top line;
- All analysis and summary tables will have the analysis population sample size for each treatment group in the column heading (ie, number of subjects) where applicable;
- Baseline is defined as the latest value collected on or before the date when the first dose of study treatment is administered. If multiple values are present for the same date, the mean of these values will be used as the baseline, except for laboratory data, where the value with the worst Common Terminology Criteria for Adverse Events (CTCAE) grade will be set as baseline. For subjects who were not treated, the baseline value will be defined as the latest value collected on or prior Day 1 of the Cycle 1 visit, if available;
- The day of first dose of study drug pomalidomide will be defined as Day 1. For subjects who are not treated, the Cycle 1 Day 1 visit will be defined as Day 1;
- For tables and figures displaying results by visit, only scheduled visits will be considered beside clinical laboratory evaluations. Unscheduled visits will appear only in listings and could be considered in some derivations;
- The title of the TLG will be centrally justified with the analysis population used directly beneath the title of the TLG, while the TLG number will be in the line directly above the TLG title. The TLG number will be preceded with the text 'Table:', 'Listing:' or 'Figure:', depending on the nature of the output;
- The TLG number will not include alphabetical values;
- The title of the TLG should not include a reference to a footnote;
- The TLG footnotes should follow the following convention for ordering footnotes:
 - Abbreviations

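### Blood counts are not entered in the database, so reported cytopenia rates are lower bounds with an unknown shortfall, and the SAP refers to laboratory data that the protocol does not collect

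*Protocol*

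**What the plan says.** **Collection.** Protocol 6.4.2.6: "Screening and other laboratory assessments will be performed locally at each scheduled visit", and "Hematology, serum chemistry and viral serology laboratory values will not be collected on the laboratory eCRF". The one route it offers is the adverse event form, for those abnormalities that count as adverse events. Values that the investigator considers significant or drug-related are noted in source documents; other out-of-range values are marked as not clinically significant on the laboratory sheet.

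**When a count is an adverse event.** Protocol 10.3 gives three routes: the abnormality leads to discontinuation; it "requires treatment, modification/ interruption of the IP dose, or any other therapeutic intervention"; or the investigator judges it clinically important, for example as organ toxicity or worsening of an existing condition. No CTCAE grade is a trigger in itself.

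**What is expected and what is to be estimated.** In the pediatric Phase 1 trial the main toxicity "was myelosuppression (decreased neutrophils, platelets, lymphocytes and anemia") (Protocol 1.2.4). The first secondary objective in Protocol Table 1 includes the rate of treatment-related toxicity.

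**What the SAP assumes.** SAP 11: "Safety measurements will include AEs, clinical laboratory information, vital sign measurements, SPM, pregnancy status, and deaths". Its Appendix A1 defines baseline as the latest value, averaged if there are several on one date, "except for laboratory data, where the value with the worst Common Terminology Criteria for Adverse Events (CTCAE) grade will be set as baseline". It also exempts laboratory evaluations from the rule that by-visit tables use scheduled visits only. Sections 11.1 to 11.7 contain no laboratory subsection.

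**The concern.** For this drug, the toxicity that matters most is defined by a number on a blood count. If the number is not kept, the trial knows of a cytopenia only when someone decides to write an adverse event. Where the plan forces an action, that decision is made in advance. Where it does not, two sites can see the same count and one reports it while the other files it. Omission works in one direction only: it lowers the rate.

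At stake are the Grade 3/4 neutropenia and thrombocytopenia tables in SAP 11.1 and 11.2, which also feed the age-group tables. Without counts, no grade or nadir can be checked in the database, and no shift from baseline can be derived. Separately, the SAP speaks of laboratory data as if they will be available, which the protocol rules out.

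**Working it through.** The plan gives no figure to reproduce. The check sets the collection rule against the rules that force a report, then sizes what is left.

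**Step 1: is there another way in?** Testing is local, and neither document names a central laboratory or data transfer for safety laboratories. Source data verification (Protocol 15.1) is described as comparing eCRF entries with source, and an unreported count has no entry. The adverse event form is the only documented route.

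**Step 2: which counts must be reported under 10.3?**

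| Finding | Action required by the plan | Captured without discretion? |
|---|---|---|
| Grade 4 neutropenia on dosing days | Table 8: interrupt | Yes |
| Grade 3 or 4 febrile neutropenia | Table 8: interrupt | Yes |
| Grade 4 neutropenia of 5 days or more in the rest week | Table 8: interrupt | Yes |
| Grade 3 or 4 platelet fall on dosing days | Table 8: interrupt | Yes |
| ANC below 1,000/mm³ or unsupported platelets below 100,000/mm³ at the next Day 1 | 7.2.1: hold the cycle | Yes, since SAP 9.7 groups delays with interruptions |
| Anemia that is transfused | Treatment given | Yes |
| Non-febrile Grade 3 neutropenia, recovered before the next Day 1 | None | No |
| Grade 4 neutropenia under 5 days in the rest week, recovered before the next Day 1 | None | No |
| Rest-week platelet fall, recovered before the next Day 1 | None | No |
| Anemia, not transfused | No Table 8 row of its own | No |

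The catch-all Table 8 row for other significant events of Grade 2 or higher applies only if the investigator decides that an interruption is needed, so it does not remove discretion from the last four rows.

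**Step 3: how much is measured but not held?** Scheduled hematology draws in Protocol Table 4:

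- Screening, End of Treatment and 28-day visit: 3
- Cycles 1-2, four per cycle: 2 × 4 = 8
- Cycles 3-12, two per cycle: 10 × 2 = 20
- Cycles 13-24, one per cycle: 12 × 1 = 12

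The maximum is 3 + 8 + 20 + 12 = 43 per subject, or 80 × 43 = 3,440 for 80 subjects. From screening through Cycle 6 it is 1 + 8 + (4 × 2) = 17. Repeat tests during toxicity (7.2.2) are extra.

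**Step 4: how large is the shortfall?** The documents give neither a true cytopenia rate nor a reporting share, so it cannot be estimated. Two things can be said.

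- *Effect of one missed subject:* 1/20 = 5 percentage points in a full stratum, 1/9 = 11 points in a stratum closed after 9 subjects, 1/80 = 1.25 points overall.
- *Illustration only, on assumed inputs:* reported rate = true rate p × captured share s. Here s = f + (1 − f)c, where f is the share forced by the *Yes* rows and c the share of the remainder that sites choose to report. Hence s is never below f. Taking s from 50% to 90%:

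| Assumed p | Reported rate | Of 80 subjects |
|---|---|---|
| 30% | 15% to 27% | 12 to 21.6, instead of 24 |
| 50% | 25% to 45% | 20 to 36, instead of 40 |

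Neither p nor s comes from the documents.

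**Step 5: the SAP side.** The laboratory baseline by worst grade and the by-visit exemption both need measured values. The cytopenia tables in SAP 11.2 do not: they identify events by MedDRA preferred term and can be run from adverse event data.

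**The case against.** The other side has a good deal to say.

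- *Much is captured anyway.* A reader might infer that myelosuppression is counted only when a site chooses to act. The documents do not support that: Table 8 and the cycle-start rule in 7.2.1 force action on the most severe and the persistent falls, and transfusion is treatment. The third route in 10.3 is also broad enough that a careful site would report many of the rest. This stands, and it confines the problem to the four *No* rows.
- *The removal of the Grade 4 anemia row was reasoned.* The amendment summary cites heavy pretreatment and the difficulty of attributing anemia to the drug. That explains the dosing rule; it does not explain leaving hemoglobin unrecorded.
- *No planned output is lost.* A reader might infer that the protocol 9.7 statement, "Cross tabulations will be provided to summarize frequencies of abnormalities", cannot be met. It sits under the adverse event heading, names no laboratory values, and can be met from adverse event data. The Appendix A1 items are general conventions, and the SAP appendices carry other text that does not fit a single-arm trial, such as p-value rounding and a randomization date. The mismatch is therefore stray wording and one general commitment in SAP 11, not a set of named tables without data.
- *The monitoring committee is blind to the counts.* This is also tempting, but its working rules are in a charter that is not among the documents, and local results remain in source.
- *The Phase 1 finding was itself AE-based.* True, so an AE-based rate is comparable in kind. It is still not a rate based on counts.

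What remains is that discretion governs a definable part of the main expected toxicity, and the database cannot show how large that part is.

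**Conclusion.** The point holds in a limited form and should be fixed; it is not critical. Cytopenia rates under the secondary safety objective are lower bounds. The direction of the error is known and its size is not: the ranges in the illustration are arithmetic on assumed inputs and should not be quoted as an estimate. In strata of 9 to 20 subjects, even one or two unreported cases move a rate visibly.

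The conclusion assumes that no unseen document provides for a transfer of local laboratory data, and that a delayed cycle counts as an interruption for 10.3, as SAP 9.7 treats it. If a delay did not count, more would rest on judgement.

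The primary endpoint, the stage decisions and the dose rules do not use laboratory eCRF data and are unaffected. The inconsistency between Protocol 6.4.2.6 and SAP 11 with Appendix A1 needs correcting either way.

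**What to change.** **Preferred.**

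1. In Protocol 10.3, require every CTCAE Grade 3 or higher ANC, platelet and hemoglobin value to be recorded as an adverse event, whether or not any action follows. No dose rule changes.
2. Preferably also enter the baseline and the lowest ANC, platelet and hemoglobin value in each cycle, with dates, from tests already done. If this is adopted part-way, enter past values from source so that the rates are not a mixture.
3. Add to SAP 11 a table of worst grade per subject and per cycle, with subjects who have a count in that cycle as denominator, and a shift table from baseline.

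**Minimum alternative.** Delete the laboratory references from SAP 11 and Appendix A1, and state that cytopenia rates are AE-reported only and are lower bounds.

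**Cost.** One sentence in 10.3, one short eCRF page and two SAP tables; no new blood draw. Lowest value per cycle plus baseline is at most 24 + 1 = 25 entries of three values per subject. Finding them means reviewing up to 43 scheduled draws and the unscheduled toxicity tests, where nadirs are likely. The reported cytopenia rate will rise, which the study report should explain. One limit remains: after Cycle 2 no Day 22 draw is scheduled, so a rest-week fall that recovers before Day 1 may never be measured.
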